1.0 BACKGROUND AND SIGNIFICANCE

The principal goal for the study is to examine whether there is a difference between the ingestion of choline through supplements versus choline found within eggs on plasma TMAO levels. We have previously shown that dietary intake of trimethylamines, including the choline group of phosphatidylcholine (PC), is mechanistically linked to cardiovascular disease risk and that the metabolism of these trimethylamine nutrients in humans is modulated by the intestinal microbes (gut microbes). Additionally, extensive animal studies link an essential role of gut microbiota to the metabolism of choline and the production of metabolites that promote / accelerate atherosclerotic processes (Wang et al, 2011, Nature). We have also recently shown a 10-fold increase in plasma TMAO levels following supplementation with choline bitartrate supplements. However, another pilot study by a collaborator did not show the same increase in plasma TMAO levels following the ingestion of whole eggs, a major dietary source of choline. Therefore, with this study we wish to examine the differences, if any, between the ingestion of an equivalent mass of total choline in the free form (as bitartrate salt) as a supplement vs. within whole eggs. We also wish to examine the ingestion of an equivalent mass of choline as a phosphatidylcholine (PC) supplement capsule and compare this to the ingestion of the choline bitartrate supplements and/or the whole eggs.

Eggs, and specifically the egg yolk, contain a large amount of total choline (USDA Database for the Choline Content of Common Foods, 2008). However, egg white contains potential antimicrobial peptides that could influence gut microbial composition and function, and therefore impact conversion of choline into TMA and TMAO observed in subjects. Therefore, we hypothesize that the consumption of whole eggs (hardboiled) will not elevate plasma TMAO levels to the same extent as a comparable amount of total choline ingested in capsule form as the choline bitartrate salt. We further hypothesize that the consumption of egg white with choline bitartrate tablets may result in less of a rise in TMAO levels than ingestion of the choline bitartrate supplement alone.

The majority of the choline present in egg yolks is found as part of phosphatidylcholine. We therefore hypothesize that the ingestion of phosphatidylcholine supplements will not elevate plasma TMAO levels to the same extent as a comparable amount of total choline ingested in capsule form as the choline bitartrate salt, but will instead elevate plasma TMAO levels in a comparable fashion to the whole eggs (hardboiled).

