3.0 STUDY DESIGN

This is a prospective non-blinded randomized study with 5 study arms as detailed below. For each study arm, subjects will be asked to consume choline bitartrate tablets, phosphatidylcholine capsules, and/or eggs or egg whites every day for 4 weeks.

Arm 1: whole hardboiled egg

Arm 2: choline bitartrate tablets

Arm 3: whole hardboiled egg + choline bitartrate tablets

Arm 4: egg whites + choline bitartrate tablets

Arm 5: phosphatidylcholine capsules

For arms 1-4, subjects will be randomly assigned to one of these study arms at the time of enrollment. For arm 5, the phosphatidylcholine arm, which we have added in version 1.2 of this protocol, subjects will not be randomized but will instead be assigned this arm until at least 10 subjects have completed this arm. We expect to enroll at least 10 subjects into each of the 5 arms of the study, up to a maximum of 100 total study participants. The large anticipated maximum enrollment accounts for any subjects who may withdraw early or who may need to be withdrawn because of antibiotic usage or non-compliance during the course of the study.

At the first (baseline) study visit, subjects will have blood and urine samples collected. Subjects will then be randomized or assigned to one of the five study arms as described above.

Following randomization, or assignment in the case of arm 5, subjects will be asked to pick up their assigned study food and/or supplements each week. Spot urine collections will be collected weekly. Subjects will also be asked to provide a stool sample at the time of the spot urine collection if they are able to. The stool samples will be optional, we will not require them.

At the day 7 visit and the final visit they will have repeat blood and urine collections. After 4 weeks of supplementation, subjects will have their final study visit. This visit will occur between 26 and 30 days after their baseline visit.

	Day 1 (Baseline)	Day 2	Day 7*	Day 8	Day 14*	Day 21*	Day 28*	Final Visit (Day 29)
Informed consent	Х							
Vital signs and brief medical history	Х		Х				Х	
Fasting Blood Draw	Х		Х				Х	
Pick up eggs and/or supplements		Х	Х		Х	Х		
Spot Urine sample	Х		Х		Х	Х	Х	
Start 24 hour urine	Х		Х				Х	
Return 24-Hour Urine		Χ		Х				Х

|--|

^{*}these study visits can occur +/- 2 days from day noted

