5.0 STUDY DRUG/BIOLOGIC

5.1 Description

Choline bitartrate and phosphatidylcholine supplements will be used in this study. These will be obtained from a commercial source and stored as below. Whole, hardboiled, prepeled eggs and egg whites will also be obtained from a commercial source and stored as below.

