5.2 Treatment Regimen

For subjects in arms 1, 3, and 4, 500 mg choline bitartrate tablets will be given to be taken daily by mouth. Subjects will be asked to take two tablets each day, one in the morning and one in the evening, for a total of 1,000 mg daily. Subjects in arm 2 will not receive any choline tablets.

For subjects in arms 2 and 3, four pre-peeled hardboiled eggs will be given to be taken daily by mouth, two in the morning and two in the evening. Subjects in arm 3 will be asked to eat the hardboiled eggs in addition to taking the choline bitartrate tablets.

For subjects in arm 4, four pre-peeled hardboiled eggs will be given and subjects will be instructed to eat only the egg whites while discarding the egg yolks. Subjects will be asked to eat two egg whites in the morning and two egg whites in the evening. Subjects in arm 4 will be asked to eat the egg whites in addition to taking the choline bitartrate tablets.

For subjects in arm 5, 420 mg phosphatidylcholine capsules will be given to be taken daily by mouth. Subjects will be asked to take 6 capsules each day, 3 in the morning and 3 in the evening, for a total of 2,520 mg daily. Subjects in arm 5 will not receive any hardboiled eggs.

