6.0 STUDY PROCEDURES

This is a prospective pilot study consisting of 5 arms. Up to 100 subjects will be enrolled across all arms in this pilot study, with a goal of having at least 10 subjects complete each arm of the study.

Arm 1: Choline Bitartrate Tablets Alone

Subjects in this arm will be asked to take two 500mg choline bitartrate tablets (for a total of 1,000mg) daily by mouth for four weeks. They will be asked to take one capsule in the morning and one in the evening. We aim to have at least 10 subjects complete this arm.

Arm 2: Whole Hardboiled Eggs

Subjects in this arm will be asked to eat four hardboiled eggs daily for four weeks. They will be asked to eat 2 eggs in the morning and 2 eggs in the evening. We aim to have at least 10 subjects complete this arm.

Arm 3: Whole Hardboiled Egg + Choline Bitartrate Tablets

Subjects in this arm will be asked to eat four hardboiled eggs and take two 500mg choline bitartrate tablets (for a total of 1,000mg) by mouth daily for four weeks. They will be asked to eat 2 eggs and take 1 capsule in the morning, and then eat 2 eggs and take 1 capsule in the evening. We aim to have at least 10 subjects complete this arm.

Arm 4: Egg Whites + Choline Bitartrate Tablets

Subjects in this arm will be asked to eat the equivalent of four egg whites and take two 500mg choline bitartrate tablets (for a total of 1,000mg) by mouth daily for four weeks. They will be asked to eat 2 egg whites and take 1 capsule in the morning, and then eat 2 egg whites and take 1 capsule in the evening. We aim to have at least 10 subjects complete this arm.

Arm 5: Phosphatidylcholine Capsules Alone

Subjects in this arm will be asked to take six 420 mg choline bitartrate tablets (for a total of 2,025 mg) daily by mouth for four weeks. They will be asked to take three capsule in the morning and three in the evening. We aim to have at least 10 subjects comlete this arm.

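### Section 6.0 gives the wrong product and total for arm 5, and the equal-choline comparison of phosphatidylcholine with bitartrate is stated but never shown

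*Combined protocol and SAP*

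**What the plan says.** Section 1.0 describes the PC comparison as "ingestion of an equivalent mass of choline as a phosphatidylcholine (PC) supplement capsule and compare this to the ingestion of the choline bitartrate supplements", and extends it to whole eggs. The first part of the PC hypothesis, also in section 1.0, is that PC supplements will not raise plasma TMAO "to the same extent as a comparable amount of total choline ingested in capsule form as the choline bitartrate salt". The second part is that PC will behave like whole eggs.

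Section 5.2 sets the doses by product:

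- Bitartrate: two 500 mg tablets, "one in the morning and one in the evening, for a total of 1,000 mg daily".
- PC (arm 5): 420 mg capsules, with subjects asked to "take 6 capsules each day, 3 in the morning and 3 in the evening, for a total of 2,520 mg daily".

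On the products, section 5.1 says only: "These will be obtained from a commercial source and stored as below". No section gives the choline content of a tablet, capsule or egg, the basis of the label strength, the purity, or a conversion factor. For eggs, section 1.0 cites a USDA choline database but takes no figure from it.

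Section 6.0 heads arm 5 as PC capsules alone, then instructs subjects to "take six 420 mg choline bitartrate tablets (for a total of 2,025 mg) daily by mouth for four weeks".

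Section 3.0 lists arm 5 as PC capsules and says that its "subjects will not be randomized but will instead be assigned this arm until at least 10 subjects have completed this arm".

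**The concern.** There are two separate problems.

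First, the arm 5 instruction in the procedures section names the wrong compound and a total that does not follow from its own count and strength. Staff work from this section.

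Second, the PC-versus-bitartrate hypothesis is about chemical form at matched choline. Equal or proportionate masses of compound do not give equal choline, because choline is a different fraction of each molecule. If the arms differ in choline, dose and form are confounded. A lower dose in the PC arm would push the contrast towards the hypothesised result, and a higher dose would push it away. Section 7.2 has no dose adjustment, so a report repeating the wording of section 1.0 would claim an equivalence that the protocol does not establish.

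**Working it through.** Arms are named by content here, because sections 5.2 and 6.0 number the egg and bitartrate arms the opposite way from section 3.0.

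**Step 1: the plan's own totals.**
- Bitartrate: 2 x 500 = 1,000 mg. This reproduces section 5.2.
- PC: 6 x 420 = 2,520 mg. This reproduces section 5.2.
- Section 6.0's 2,025 mg does not reproduce. It would need units of 2,025/6 = 337.5 mg, or 2,025/420 = 4.8 units. Transposed digits are the likely cause.

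**Step 2: convert to choline.** The documents give no molecular weights. Assumed values (g/mol) are choline 104.17, choline bitartrate 253.25 and PC 734-810. Choline mass = compound mass x 104.17 / molecular weight of the compound.
- Bitartrate: 104.17/253.25 = 41.1%, so 1,000 mg gives 411.3 mg.
- PC: 104.17/810 to 104.17/734 = 12.9% to 14.2%, so 2,520 mg gives 324.1 to 357.6 mg.
- Ratio: 324.1/411.3 = 0.788 and 357.6/411.3 = 0.869, so PC supplies 13-21% less.

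A wider PC range of 700-850 gives 375 to 309 mg, or 91% to 75% of the bitartrate dose.

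**Step 3: vary the label reading.**

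| Reading | Tablets, mg choline | Capsules, mg choline | PC relative to tablets |
|---|---|---|---|
| Pure compounds (main case) | 411.3 | 324.1-357.6 | 13-21% less |
| PC is 15% choline by mass | 411.3 | 378 | 8% less |
| Capsules 90% PC | 411.3 | 291.7-321.9 | 22-29% less |
| Capsules 50% PC | 411.3 | 162.0-178.8 | 57-61% less |
| 500 mg is choline itself | 1,000 | 324.1-357.6 | 64-68% less |
| 500 mg is tablet weight, 75% salt | 308.5 | 324.1-357.6 | 5-16% more |

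The last row is 0.75 x 411.3 = 308.5, then 324.1/308.5 = 1.05 and 357.6/308.5 = 1.16. With pure PC capsules, the arms would match if tablets were 79-87% salt by weight (324.1/411.3 to 357.6/411.3).

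**Step 4: what parity needs if both products are pure.** 411.3/2,520 = 16.3% choline, a PC molecular weight of 104.17/0.1632 = 638, which is below the assumed range. Per capsule, parity needs 411.3/6 = 68.6 mg choline.

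**Step 5: section 6.0 taken literally.** Six 420 mg bitartrate tablets are 2,520 mg of salt: 2,520 x 0.411 = about 1,037 mg choline, 2.52 times the bitartrate-alone dose. At the printed 2,025 mg the figure is about 833 mg, or 2.0 times.

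**The case against.** The strongest objection is that the documents do not settle the direction of any choline difference. A reader might infer that the PC arm certainly receives less choline and that the contrast is therefore biased towards the hypothesis. That goes too far. Section 5.2 words the two strengths in parallel, so if capsules may contain less than 420 mg of PC, tablets may equally contain less than 500 mg of salt. The last row of the table reverses the sign. This objection stands, so the bias is conditional.

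A reader might also infer that arm 5 will be given 2 to 2.5 times the bitartrate dose. This is unlikely. No 420 mg bitartrate tablet appears anywhere else in the protocol, and the arm's heading and sections 3.0 and 5.2 all say PC capsules. The error is clerical, but it sits in an operative dosing instruction and still needs correcting.

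On impact, it can be said that a gap of 8-21% still counts as comparable, that this is a pilot, and that the section 2.0 objective is a before-and-after comparison within subjects. Section 1.0 also mentions a 10-fold TMAO increase with bitartrate. If that applied here and the rise were proportional to dose (neither is established, and that study's dose is not given), 79-87% of the choline would give a level of 1 + 9 x 0.788 = 8.1 to 1 + 9 x 0.869 = 8.8 times baseline. This supports a lower severity. It does not supply the missing conversion, and section 1.0 also uses the stricter term, equivalent mass.

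Finally, PC is also to be compared with eggs. Matching capsules to tablets alone could unbalance that comparison, so any dose change must consider egg choline too. No egg-versus-tablet mismatch is claimed here, because the documents give no egg choline figure to test.

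**Conclusion.** The point holds in two parts. The section 6.0 error is certain from the documents alone: wrong product, and 2,025 mg where the arithmetic and section 5.2 give 2,520 mg. It is also certain that section 1.0 claims equivalent or comparable choline while section 5.2 doses by compound with no conversion anywhere.

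The size of the mismatch is conditional. Reading section 5.2 as pure compound, with the assumed molecular weights, PC delivers 13-21% less choline. Other label readings run from 68% less to 16% more. The effect on TMAO cannot be sized reliably, since the plan gives no dose-response and no SD.

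Matched choline would not by itself make this a clean test of chemical form. Arm 5 is not randomized, as section 3.0 openly states, and that is a larger limit on the same contrast. Severity is minor to should-fix.

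**What to change.** 1. In section 6.0, correct arm 5 to six 420 mg PC capsules, total 2,520 mg/day.
2. Add a table of total choline per day for each arm, covering tablets, capsules and eggs, from product certificates and the USDA database already cited. State whether each label strength refers to choline, compound or unit weight.
3. In section 1.0, replace the equivalence wording for PC with the actual choline doses, and limit the PC-versus-bitartrate conclusion to those doses.
4. Change the capsule count only if arm 5 dosing has not begun, and only after weighing egg choline as well as tablet choline. If dosing has begun, keep the dose, because a change would mix doses within an arm of about 10 subjects.

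The cost is one corrected paragraph, one table and a wording change. No subjects, visits or assays are added.

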2.0 STUDY OBJECTIVES

To compare the blood and urine levels of free choline, phosphatidylcholine (PC), trimethylamine-N-oxide (TMAO), trimethylamine (TMA), and gammabutyrobetaine in subjects before versus following the ingestion of choline provided in either the bitartrate salt (in supplement) form, within phosphatidylcholine (in supplement form), within eggs (whole or in part), or in combinations of these.

3.0 STUDY DESIGN

This is a prospective non-blinded randomized study with 5 study arms as detailed below. For each study arm, subjects will be asked to consume choline bitartrate tablets, phosphatidylcholine capsules, and/or eggs or egg whites every day for 4 weeks.

Arm 1: whole hardboiled egg

Arm 2: choline bitartrate tablets

Arm 3: whole hardboiled egg + choline bitartrate tablets

Arm 4: egg whites + choline bitartrate tablets

Arm 5: phosphatidylcholine capsules

For arms 1-4, subjects will be randomly assigned to one of these study arms at the time of enrollment. For arm 5, the phosphatidylcholine arm, which we have added in version 1.2 of this protocol, subjects will not be randomized but will instead be assigned this arm until at least 10 subjects have completed this arm. We expect to enroll at least 10 subjects into each of the 5 arms of the study, up to a maximum of 100 total study participants. The large anticipated maximum enrollment accounts for any subjects who may withdraw early or who may need to be withdrawn because of antibiotic usage or non-compliance during the course of the study.

At the first (baseline) study visit, subjects will have blood and urine samples collected. Subjects will then be randomized or assigned to one of the five study arms as described above.

Following randomization, or assignment in the case of arm 5, subjects will be asked to pick up their assigned study food and/or supplements each week. Spot urine collections will be collected weekly. Subjects will also be asked to provide a stool sample at the time of the spot urine collection if they are able to. The stool samples will be optional, we will not require them.

At the day 7 visit and the final visit they will have repeat blood and urine collections. After 4 weeks of supplementation, subjects will have their final study visit. This visit will occur between 26 and 30 days after their baseline visit.

	Day 1 (Baseline)	Day 2	Day 7*	Day 8	Day 14*	Day 21*	Day 28*	Final Visit (Day 29)
Informed consent	Х							
Vital signs and brief medical history	Х		Х				Х	
Fasting Blood Draw	Х		Х				Х	
Pick up eggs and/or supplements		Х	Х		Х	Х		
Spot Urine sample	Х		Х		Х	Х	Х	
Start 24 hour urine	Х		Х				Х	
Return 24-Hour Urine		Χ		Х				Х

|--|

^{*}these study visits can occur +/- 2 days from day noted

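### In this open-label study, allocation appears to fall on Day 1, before the baseline 24-hour urine is completed on Day 2, so that one baseline sample can be collected with the arm known

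*Combined protocol and SAP*

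**What the plan says.** All the relevant text is in Section 3.0 of the combined protocol and SAP.

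- Blinding: "This is a prospective non-blinded randomized study with 5 study arms".
- First statement on timing, for arms 1 to 4: "subjects will be randomly assigned to one of these study arms at the time of enrollment".
- Baseline sampling: "At the first (baseline) study visit, subjects will have blood and urine samples collected".
- Second statement on timing, directly after the sampling sentence: "Subjects will then be randomized or assigned to one of the five study arms as described above".
- Arm 5: "subjects will not be randomized but will instead be assigned this arm until at least 10 subjects have completed this arm".
- Schedule table: consent, fasting blood and spot urine are on Day 1. The row "Start 24 hour urine" is marked on Day 1 and the row "Return 24-Hour Urine" on Day 2. Product is first picked up on Day 2. There is no row for randomisation or for telling subjects their arm.

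On diet, Section 4.1 asks only that subjects can stay off other supplements. Section 6.1 lists no diet record, and no section asks subjects to keep their usual diet during the baseline period.

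**The concern.** A baseline serves as a fair reference for change only if it cannot depend on the assigned arm. Blood and spot urine are taken at one moment. A 24-hour urine depends on what the subject eats over the following day and on how carefully every void is kept, and both are under the subject's control.

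Section 1.0 calls whole eggs a major dietary source of choline, and they are an ordinary food. A subject told on Day 1 to expect four eggs a day might skip eggs until then or begin early; a subject told to expect tablets has less reason to do either. Motivation to collect completely may also differ by arm when the assignment is known and perhaps unwelcome.

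Two things are at stake. The first is comparability of the 24-hour urine baseline across arms: Section 2.0 makes urine levels before and after ingestion an objective, and Section 3.1 lists percent-rise calculations in urine. The second is that a subject can be randomised and then never supply this sample. Section 7.2 gives no rule for a missing baseline.

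**Working it through.** **Order of events.** The plan gives no figure on this point, so the check sets the text beside the schedule.

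1. Consent is on Day 1, so enrolment is naturally read as Day 1. The first statement then puts randomisation of arms 1 to 4 on Day 1.
2. The second statement follows the sentence about samples at the first visit, which the table labels Day 1. It also puts allocation on Day 1, but after those samples.
3. A 24-hour collection that starts on Day 1 cannot be complete at the Day 1 visit. The schedule confirms this by placing its return on Day 2.
4. From 1 to 3, the likely sequence is: consent, fasting blood and spot urine; allocation; most or all of the 24-hour urine; urine return and product pick-up on Day 2.
5. Nothing in the plan withholds the arm from the subject between allocation and Day 2.

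| Baseline sample | Day | Relative to allocation, second statement | Relative to allocation, first statement alone |
|---|---|---|---|
| Fasting blood | 1 | Before | Not clear |
| Spot urine | 1 | Before | Not clear |
| 24-hour urine | 1 to 2 | Mostly or wholly after | Mostly or wholly after |

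Only the 24-hour urine is exposed under both statements. Product is not supplied until the day that urine is returned, so the route of bias is behaviour, not study product.

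**What a shifted baseline would do (illustration only).** Let R be the true ratio of follow-up to baseline excretion, and d the fraction by which the 24-hour baseline is lowered in one arm. The observed percent rise is R/(1 − d) − 1. Both R and d are assumptions; the documents give neither for urine. With R = 2, a true rise of 100%:

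| d | Calculation | Observed rise |
|---|---|---|
| 5% | 2/0.95 − 1 | 111% |
| 10% | 2/0.90 − 1 | 122% |
| 20% | 2/0.80 − 1 | 150% |
| −10% (baseline raised) | 2/1.10 − 1 | 82% |

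On the ratio scale the distortion is 1/(1 − d) whatever R is, for example 1/0.90 = 1.11. The last row shows that the sign depends on which way behaviour changes.

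**Missing baselines.** The plan aims for at least 10 completers per arm (Section 6.0). One randomised subject without a 24-hour baseline would be 1/10 = 10% of an arm of that size for this measure.

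**The case against.** The strongest reply has five parts.

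- *The two timing statements describe one event.* The later sentence refers back to the earlier one, and its order is explicit: samples, then allocation. This stands for the blood and the spot urine. A reader might infer from the first statement that the whole baseline, plasma included, is exposed. The second statement does not support that.
- *The 24-hour urine is not the only urinary reference.* This also stands. Section 3.1 speaks of fasting urine levels and serial changes without naming the 24-hour collection. The schedule has spot urine on five days (1, 7, 14, 21, 28) and starts 24-hour collections on three (1, 7, 28). It would be tempting to say that every urinary change endpoint is affected, but no section says so.
- *The plan does not say when subjects learn their arm.* True. The baseline urine samples in the text could also be meant to include the 24-hour urine, which would put allocation on Day 2. But the text places those samples at the first visit, which is Day 1, and the schedule has no entry to settle it. Exposure is therefore the natural reading, not an established fact.
- *Any bias may be conservative.* If subjects in the egg arms cut back on eggs, their percent rise is inflated, which works against the Section 1.0 hypotheses that those arms rise less. This holds for that one behaviour only. Eating eggs early, or collecting incompletely in another arm, could push the other way.
- *A subject who does not return on Day 2 still has baseline plasma and spot urine, and enrolment allows for withdrawals.* Both are correct. Extra enrolment replaces numbers, however, and does not undo a loss that depends on the arm.

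**Conclusion.** The point holds for one sample. On the natural reading of Section 3.0, the baseline 24-hour urine is collected after an open-label allocation, so it could shift by arm and could be missing in a randomised subject. The principal plasma TMAO comparison is not affected, because the Day 1 fasting blood precedes allocation under the second timing statement. The spot urine baseline is protected in the same way.

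The conclusion assumes that allocation takes place at the Day 1 visit and that subjects may be told then; the plan states neither outright. The size and direction of any bias are unknown. The illustrative rises of 82% to 150% against a true 100% come from assumed inputs and are not estimates for this trial.

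The change is still worth making: the exposure is avoidable, the remedy alters how the trial is run and not just its wording, and it costs almost nothing.

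**What to change.** Replace the two timing statements in Section 3.0 with one rule and add a matching row to the schedule on Day 2. Suggested content:

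- Confirm eligibility and consent, and take the fasting blood and spot urine, on Day 1. Start the 24-hour urine on Day 1 with the arm not yet allocated.
- On Day 2, once the 24-hour urine has been returned, randomise subjects in arms 1 to 4 and tell them their arm immediately before product pick-up.
- Ask all subjects to keep their usual diet from Day 1 until allocation.

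Arm 5 may be assigned at the same point. Because it is filled without randomisation, its assignment may be predictable at consent. Moving the step does not conceal it, and the protocol should say so.

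The cost is an amendment to the text and the schedule, and moving the allocation step to the Day 2 visit that already exists for urine return and product pick-up. No visit or sample is added. A subject who does not return on Day 2 would then not have been randomised.
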